5.3. Inclusion Criteria: Part B, Participants with PAH

Participants are eligible to be included in this study only if all of the following criteria apply:

Age and Sex:

- 1. Participants aged ≥18 years (or the minimum age of consent in accordance with local regulations) at screening who have signed informed consent.
 - Refer to Appendix 4 for reproductive criteria for male (Section 10.4.1) and female (Section 10.4.2) participants.

Disease Characteristics:

- 2. Documented diagnostic RHC prior to Screening confirming diagnosis of PAH (WHO Group 1 PH) including any of the following subtypes:
 - Idiopathic or heritable PAH.
 - Drug- or toxin-induced PAH.
 - PAH associated with connective tissue disease.
 - PAH associated with simple, congenital systemic-to-pulmonary shunts at least 1 year following shunt repair.
- 3. PAH classified as WHO functional class II or III.
- 4. Pre-randomization RHC documenting a minimum of $PVR \ge 400 \text{ dyn} \cdot \text{sec/cm}^5$ (5 Wood units); and no contraindication to RHC.
 - RHC performed within 12 weeks of Screening as part of the participants management of PAH can satisfy this criterion, if the requisite hemodynamic data are available. Otherwise, a RHC needs to be performed prior to randomization. In this case, the RHC should only be performed if the potential participant meets all other inclusion / exclusion criteria for eligibility.

- 5. PFTs (spirometry) performed as part of the diagnostic evaluation of PAH excluding clinically relevant obstructive or restrictive pulmonary physiology (unless the participant is an active smoker of > 10 cigarettes/equivalent per day or a smoking history ≥ 10 pack-years, in which case, the PFTs should be done within 6 months prior to Screening). A high-resolution chest computed tomography within 1 year of Screening indicating no more than minimum emphysematous or interstitial changes may be used to satisfy this requirement.
- 6. Documentation in the participant's medical history that CTEPH has been excluded.
- 7. $6MWD \ge 150$ m and ≤ 500 m repeated at least twice during Screening and top two values within 15% of each other, calculated from the highest value.
- A stable dose of at least 2 SOC PAH vasodilator class therapies (as defined in Section 6.9.5) for 60 days prior to Screening (for infusion prostacyclins, dose adjustment within 10% of optimal dose is allowed per medical practice)

Other Inclusion Criteria:

- 9. BMI 16 to 35 kg/m².
- 10. Participants who are willing and able to comply with all scheduled visits, treatment plan, laboratory tests, lifestyle considerations, and other study procedures.

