Visit Window			±1 day	±2 days	±2 days	±2	±2 days	±2 days	±2 Days		 All screening should be done ≤35 days before the first dose. A delay in randomization ≤ 7 days due to the need to acquire RHC, PFT and /or repeat laboratory data will not be considered as a PD. See Section 8.4.3 for follow-up AE and SAE assessments.
											 RHC. Pre- randomization RHC should be done within 2 weeks of randomization. Data from a RHC performed within 12 weeks of Screening as part of the participant's usual disease monitoring may satisfy this requirement provided all required data are available. The EOT RHC may be performed within -10 /

Visit Identifier Abbreviations used in this table may be found in Appendix10.							Trea	itment	Period	Early Discontinuation	Notes
Days relative to Day 1	Screen (Up to 35 days before Day 1)	Day 1	Day 8	Day 29	Day 57	Day 85	Day 113	Day 141	Day 169		• Day relative to start of study intervention (Day 1).
			Week 1	Week 4	Week 8	Week 12	Week 16	Week 20	Week 24 / EOT		
Visit Window			±1 day	±2 days	±2 days	±2 days	±2 days	±2 days	±2 Days		 All screening should be done ≤35 days before the first dose. A delay in randomization ≤ 7 days due to the need to acquire RHC, PFT and /or repeat laboratory data will not be considered as a PD. See Section 8.4.3 for follow-up AE and SAE assessments.
											+5 days of the nominal Week 24 visit.See Section 8.2.1 for additional information.
Contraception check	Х	Х	Х	Х	Х	Х	Х	Х	Х	Х	

Visit Identifier Abbreviations used in this table may be found in Appendix10.							Trea	atment	Period	Early Discontinuation	Notes
Days relative to Day 1	Screen (Up to 35 days before Day 1)		8	Day 29	Day 57	Day 85	Day 113	Day 141	Day 169		• Day relative to start of study intervention (Day 1).
			Week 1	Week 4	Week 8	Week 12	Week 16	Week 20	Week 24 / EOT		
Visit Window Laboratory Assessments			±1 day	±2 days	±2 days	±2 days	±2 days	±2 days	±2 Days		 All screening should be done ≤35 days before the first dose. A delay in randomization ≤ 7 days due to the need to acquire RHC, PFT and /or repeat laboratory data will not be considered as a PD. See Section 8.4.3 for follow-up AE and SAE assessments. See Section 8.3.5 for
											 additional information. See Appendix 2 for a list of Clinical Laboratory tests to be done. For laboratory collection volumes, see the laboratory manual.

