- 4. Initiation of an exercise program for cardiopulmonary rehabilitation within 90 days prior to Screening or planned initiation during the study (participants who are stable in the maintenance phase of a program and who will continue for the duration of the study are eligible).
- 5. PCWP/ Pulmonary Arterial Occlusion Pressure (PAOP) > 15 mmHg on RHC conducted during Screening.
- 6. Any current or prior history of symptomatic coronary disease (prior myocardial infarction, percutaneous coronary intervention, coronary artery bypass graft surgery, or cardiac anginal chest pain).
- 7. Acutely decompensated heart failure within 30 days prior to Screening, as per investigator assessment.
- 8. Significant (\geq 2+ regurgitation) mitral regurgitation (MR) or a ortic regurgitation (AR) valvular disease.
- 9. History of severe allergic or anaphylactic reaction or hypersensitivity to recombinant proteins or excipients in investigational product.
- 10. Major surgery within 8 weeks prior to randomization. Participants must have completely recovered from any previous surgery prior to randomization.
- 11. Prior heart or heart-lung transplants, active on the lung transplant list, or life expectancy of < 12 months.
- 12. History of active malignancy, with the exception of fully excised or treated basal cell carcinoma, cervical carcinoma in-situ, or ≤ 2 squamous cell carcinomas of the skin.
- 13. History of clinically significant (as determined by the investigator) non-PAH related cardiac, endocrine, hematologic, hepatic, immune, metabolic, urologic, pulmonary, neurologic, neuromuscular, dermatologic, psychiatric, renal, and/or other disease that may limit participation in the study.

Prior/Concomitant Therapy:

14. Current use of any prohibited concomitant medication(s) or participants unwilling or unable to use a required concomitant medication(s). Refer to Section 6.9.

Prior/Concurrent Clinical Study Experience:

15. Previous administration with an investigational drug within 30 days (or as determined by the local requirement) or 5 half-lives preceding the first dose of study intervention used in this study (whichever is longer) and not concurrently involved in a clinical trial with another investigational product during the study.

Diagnostic Assessments:

- 16. Uncontrolled systemic hypertension as evidenced by sitting systolic BP > 160 mm Hg or sitting diastolic BP > 100 mm Hg during Screening after a period of rest.

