8.2.1. Pulmonary Vascular Resistance by Right Heart Catheterization

Pulmonary vascular resistance (PVR) will be measured by right heart catheterization (RHC) during the Screening period and at the Week 24 visit in accordance with the site's/investigators standard practice (SOPs). The RHC should be performed after confirmation of all other eligibility criteria and within 2 weeks of randomization. The RHC may be performed within -10 to + 5 days of the Week 24 visit. Data from RHC performed as part of the participant's usual medical care or as part of the diagnostic assessment of PAH within 12 weeks of signing the ICD may be used to assess eligibility, provided required data are available for entry into the CRF.

In addition to PVR, the RHC will also assess the following hemodynamic variables:

- RAP, mean PAP, mean PCWP / PAOP, RV SBP, RV DBP, HR
- CO is measured in triplicate either by the Fick method or by the thermodilution method. The same method is to be used at the Screening and Week 24 or ED visits.

These hemodynamic parameters are to be assessed when the participant is at a stable hemodynamic rest state which is defined as 3 consecutive mean PAP and CO measurements within 10% of each other.

PVR is to be calculated and entered in the CRF.

The acquired RHC data, as available, may be reviewed centrally to confirm pulmonary vascular hemodynamic measurements. If performed, details of the central review will be provided separately.

8.2.2. 6-Minute Walk Test

The 6MWT is a submaximal exercise test that entails measurement of distance walked over a span of 6 minutes.¹⁸ The 6MWD (distance traveled in meters) provides a measure for integrated global response of multiple cardiopulmonary and musculoskeletal systems involved in exercise. The 6MWT should be performed in accordance with the PI's usual procedure. The 6MWT is to be performed at least twice during the Screening Period at least 4 hours (but no longer than 1 week) apart and distances must be within 15% of each other, calculated from the higher number. The 6MWT is to be performed at Screening, and as additional time points per SoA. If occurring on the same day, 6MWT should be performed before RHC. Detailed instructions on conducting the 6MWT will be provided separately.

The Borg CR10 scale® will be completed before and after each 6MWT as specified in the SoA. (See Section 8.2.4.6.)

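### The wedge-pressure exclusion does not reach participants who qualify on an RHC done before Screening, and that RHC can also predate the last change in background PAH therapy

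*Protocol*

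**What the plan says.** **Which RHC may qualify a participant.** Protocol 5.3, criterion 4 (repeated in synopsis 1.1.3), requires a pre-randomization RHC showing the minimum PVR and adds: "RHC performed within 12 weeks of Screening as part of the participants management of PAH can satisfy this criterion". A new RHC is needed only if no such record exists. The RHC note in the Part B Schedule of Activities (Table 3) says that data from "usual disease monitoring may satisfy this requirement provided all required data are available". Section 8.2.1 repeats the allowance with a different anchor: data from usual care or from the diagnostic assessment "within 12 weeks of signing the ICD may be used to assess eligibility, provided required data are available for entry into the CRF".

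**Timing of a study RHC.** Section 8.2.1: "The RHC should be performed after confirmation of all other eligibility criteria and within 2 weeks of randomization".

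**Wedge pressure.** Section 5.4, exclusion 5 (exclusion 4 in synopsis 1.1.4), excludes "PCWP/ Pulmonary Arterial Occlusion Pressure (PAOP) > 15 mmHg on RHC conducted during Screening".

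**Background therapy.** Section 5.3, criterion 8, requires "A stable dose of at least 2 SOC PAH vasodilator class therapies (as defined in Section 6.9.5) for 60 days prior to Screening". Section 6.9.5 gives the same 60 days.

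**Use of PVR.** Change in PVR at Week 24 is a secondary endpoint with its own estimand, E2 (3.2 and 9.1.3.2). The model in 9.3.3.1.1 uses the pre-baseline and Week 24 values, and the PD-Hemodynamic set in 9.2 needs both.

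**The concern.** The protocol opens two routes to eligibility, an RHC done in Screening and an RHC done in usual care beforehand, but words the wedge-pressure exclusion for the first route only. A site that follows the text exactly has no stated ground to exclude a participant whose historical RHC shows a wedge pressure above the limit, although the same result on a Screening RHC would exclude that person. The trial evidently means to exclude such participants whichever RHC shows it.

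The historical RHC also raises a measurement question. The look-back for the RHC is longer than the period of required stability in background vasodilators, and nothing ties one to the other. If therapy was started or changed after that RHC, part of the recorded change in PVR to Week 24 reflects background treatment. At stake is the precision of a secondary endpoint planned around 15 evaluable participants per arm (9.5).

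**Working it through.** **1. Does the exclusion reach a historical RHC?**

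- Criterion 4 places the historical RHC before Screening, and the Schedule of Activities lets it stand in for the pre-randomization RHC.
- Exclusion 5 is limited to an RHC conducted during Screening.
- A participant who enters by the historical route has no RHC during Screening, so the condition in exclusion 5 cannot be met, whatever the wedge pressure was.

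Other criteria that might close the gap:

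- Criterion 2 requires a documented diagnostic RHC confirming WHO Group 1 PAH, and the background definition in 2.2 includes a wedge pressure of at most 15 mmHg. If the diagnostic RHC is also the qualifying RHC, this largely covers the case. But criterion 2 sets no age limit, and the diagnostic RHC may be a different and much older procedure.
- Section 5.4 also excludes significant mitral or aortic regurgitation and restrictive or congestive cardiomyopathy. These lower the chance of a raised wedge pressure but do not test the qualifying RHC.

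**2. Is the historical RHC the PVR baseline?** Section 8.2.1 names eligibility as its use, so this is an inference. It is a firm one: the Schedule of Activities provides one pre-treatment RHC, the historical RHC can satisfy it, and both the PVR model and the analysis set need a pre-treatment value. No other would exist for these participants.

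**3. The two windows.**

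- RHC look-back: 12 × 7 = 84 days before Screening (5.3).
- Required vasodilator stability: 60 days before Screening (5.3, 6.9.5).
- Difference: 84 − 60 = 24 days, that is, days 61 to 84.
- Share of the look-back: 24/84 = 29%. This is a share of the window, not of participants.

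Exclusion 2 in 5.4 does not close this gap. It concerns stopping supportive therapy within 90 days, not starting or changing a vasodilator.

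**4. Age of the baseline at Day 1.** Screening lasts up to 35 days (4.1.2), and a 7-day delay is not a deviation (5.6).

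- 84 + 35 = 119 days (17 weeks).
- 84 + 35 + 7 = 126 days (18 weeks).
- A study RHC: within 14 days of randomization.

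The 126 days illustrate the ordinary rules and are not a cap: 8.1 allows Screening to exceed 35 days after unexpected delays without rescreening.

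**5. Scale of a chance imbalance (illustration only).** The documents do not give the size of a background-therapy effect or the SD of log-PVR change. Assume that therapy after the RHC lowers PVR by 25%, that the SD is 0.30, that there are 15 per arm, and that one arm has two more such participants than the other.

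- Shift in the arm difference: |ln(0.75)| × 2/15 = 0.288 × 0.133 = 0.038 on the log scale, or 1 − exp(−0.038) = 3.8%.
- Standard error of the difference: 0.30 × √(2/15) = 0.11.
- Ratio: 0.038/0.11, about one third of a standard error.
- Range, lower end: a 15% reduction with SD 0.35 gives |ln(0.85)| × 2/15 = 0.022 against 0.35 × √(2/15) = 0.128, ratio 0.17.
- Range, upper end: a 35% reduction with SD 0.25 gives |ln(0.65)| × 2/15 = 0.057 against 0.25 × √(2/15) = 0.091, ratio 0.63.

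**The case against.** The strongest reply on wedge pressure is that the gap is a slip of wording with clinical cover around it: criterion 2, the PAH definition and the valve and cardiomyopathy exclusions make a raised wedge pressure unlikely, and most investigators would apply the limit anyway. That stands as a reason to expect few cases. It does not make the exclusion apply, because none of those criteria tests the RHC on which the participant qualifies. A reader might infer that the protocol lets in patients with left-heart disease generally; the documents do not support that.

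On the PVR baseline, four replies have force:

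- The 12-week allowance is deliberate. It appears in 1.1.3, 5.3, the Schedule of Activities and 8.2.1, and it spares patients a repeat invasive procedure whose listed risks (2.3.1) include bleeding, arrhythmia, lung collapse and death.
- Section 8.2.1 speaks only of eligibility, and the analysis plan, not examined here, may define the PVR baseline. That stands as to the definition, but an analysis plan cannot supply a measurement that was never taken.
- A reader might infer a biased treatment effect. The documents do not support it: Part B is randomized 1:1 and double-blind, so participants with such baselines fall into the arms by chance.
- A reader might want an inflation figure for the variance of PVR change. It would need the share of participants affected, which the documents do not give. Even 30% of all participants would require RHC dates to cluster in a stretch that is only 29% of the window. No such figure is offered here.

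**Conclusion.** The wedge-pressure point holds on the text. Exclusion 5 does not reach a participant who qualifies on an RHC done before Screening, and the cover from criterion 2 is partial. How many participants this would affect cannot be derived from the documents. The wording is nevertheless wrong for what the trial evidently intends, and correcting it costs almost nothing.

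The PVR point is secondary and modest. The 24-day mismatch is exact; use of the historical RHC as baseline is a firm inference. The consequence is added noise and possible chance imbalance in a secondary endpoint. Under the stated assumptions, an imbalance of two participants moves the PVR difference by about a third of its standard error (0.17 to 0.63 over the range shown). The primary NT-proBNP endpoint is unaffected: it does not use the RHC, and it is sampled on Day 1. Power in 9.5 rests on NT-proBNP and does not change.

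**What to change.** 1. **Exclusion 5 in 5.4 (exclusion 4 in 1.1.4).** Make it apply, with its threshold unchanged, to whichever pre-randomization RHC qualifies the participant, historical or done in Screening. Cost: one phrase in two places.
2. **Window anchor.** Use one reference point for the 12 weeks. Sections 1.1.3, 5.3 and the Schedule of Activities count from Screening; 8.2.1 counts from signing the consent document. Cost: wording only.
3. **RHC window and therapy stability.** The sponsor should reconcile the two periods so that the RHC used as PVR baseline reflects the stable background regimen, and should say in 8.2.1 whether a historical RHC serves as that baseline. One way is to accept a historical RHC only if the PAH regimen has been unchanged since it was done. Align 1.1.3, 5.3, the Schedule of Activities note and 8.2.1.

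The third change has a real downside: a few candidates would undergo the Screening RHC already in the plan, an invasive procedure, when they would otherwise have relied on a recent one. The sponsor should weigh that against a modest gain in the precision and interpretability of a secondary endpoint. The first two changes carry no such cost and need not wait for it.

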5.4. Exclusion Criteria: Part B, Participants with PAH

Participants are excluded from the study if any of the following criteria apply:

Medical Conditions:

- 1. Any medical or psychiatric condition including recent (within the past year) or active suicidal ideation/behavior or laboratory abnormality that may increase the risk of study participation or, in the investigator's judgment, make the participant inappropriate for the study.
 - Participants with seasonal allergic disease or with allergic reactions to a single avoidable allergen (eg, peanuts, bee stings) may be eligible.
 - History of HIV infection, HIV infection associated with PAH; active or latent infection with hepatitis B, or hepatitis C; positive testing for HIV, HBsAg, or HCVAb. Hepatitis B vaccination is allowed. (People with a history of hepatitis C with documentation of completion of treatment and deemed to be cured are eligible.) See Section 8.3.11 for details on testing for hepatitis.

- Evidence of active, latent, or inadequately treated infection with Mycobacterium TB as defined by either of the following:
 - A positive IGRA (eg, QuantiFERON-TB Gold In-tube, T-Spot, or equivalent test) should be performed within the 12 weeks prior to screening. If the laboratory reports the test as indeterminate, the test should be repeated.
 - History of either untreated or inadequately treated latent or active TB infection, or current treatment for the same.
- Known history of portal hypertension or chronic liver disease, including hepatitis Band/or hepatitis C (with evidence of recent infection and/or active virus replication), defined as mild to severe hepatic impairment (Child-Pugh Class A-C).
- History of more than mild, treated, obstructive sleep apnea.
- History of known pericardial constriction.
- History of recent cerebrovascular accident (CVA) within 3 months of Day 1.
- History of restrictive or congestive cardiomyopathy.
- History of personal or family history of long QTc syndrome or sudden cardiac death.
- 2. Stopped receiving pulmonary hypertension chronic general supportive therapy (eg, diuretics, oxygen, anticoagulants, digoxin) within 90 days prior to Screening.
- 3. History of atrial septostomy within 180 days prior to Screening.
- 4. Initiation of an exercise program for cardiopulmonary rehabilitation within 90 days prior to Screening or planned initiation during the study (participants who are stable in the maintenance phase of a program and who will continue for the duration of the study are eligible).
- 5. PCWP/ Pulmonary Arterial Occlusion Pressure (PAOP) > 15 mmHg on RHC conducted during Screening.
- 6. Any current or prior history of symptomatic coronary disease (prior myocardial infarction, percutaneous coronary intervention, coronary artery bypass graft surgery, or cardiac anginal chest pain).
- 7. Acutely decompensated heart failure within 30 days prior to Screening, as per investigator assessment.
- 8. Significant (\geq 2+ regurgitation) mitral regurgitation (MR) or a ortic regurgitation (AR) valvular disease.
- 9. History of severe allergic or anaphylactic reaction or hypersensitivity to recombinant proteins or excipients in investigational product.
- 10. Major surgery within 8 weeks prior to randomization. Participants must have completely recovered from any previous surgery prior to randomization.
- 11. Prior heart or heart-lung transplants, active on the lung transplant list, or life expectancy of < 12 months.
- 12. History of active malignancy, with the exception of fully excised or treated basal cell carcinoma, cervical carcinoma in-situ, or ≤ 2 squamous cell carcinomas of the skin.
- 13. History of clinically significant (as determined by the investigator) non-PAH related cardiac, endocrine, hematologic, hepatic, immune, metabolic, urologic, pulmonary, neurologic, neuromuscular, dermatologic, psychiatric, renal, and/or other disease that may limit participation in the study.

Prior/Concomitant Therapy:

14. Current use of any prohibited concomitant medication(s) or participants unwilling or unable to use a required concomitant medication(s). Refer to Section 6.9.

Prior/Concurrent Clinical Study Experience:

15. Previous administration with an investigational drug within 30 days (or as determined by the local requirement) or 5 half-lives preceding the first dose of study intervention used in this study (whichever is longer) and not concurrently involved in a clinical trial with another investigational product during the study.

Diagnostic Assessments:

- 16. Uncontrolled systemic hypertension as evidenced by sitting systolic BP > 160 mm Hg or sitting diastolic BP > 100 mm Hg during Screening after a period of rest.
- 17. Systolic BP < 90 mmHg during Screening or at baseline.
- 18. ECG with QTcF >490 msec during Screening or Randomization.
- 19. Any of the following clinical chemistry values during Screening:
 - ALT or AST > $3 \times$ ULN (> 5 ULN if solely due to right heart failure) or total bilirubin $\ge 2 \times$ ULN (For Gilbert's syndrome, direct bilirubin >ULN [or $\ge 2 \times$ ULN if solely due to right heart failure] is exclusionary).

- eGFR < 30 mL/min/1.73 m2 within 30 days prior to randomization or required renal replacement therapy within 90 days of randomization.
- 20. Hematologic abnormalities defined as:
 - Platelets \leq 50,000/mm³

Other Exclusion Criteria:

- 21. A positive urine drug test. A single repeat for positive drug screen may be allowed. A positive test for cannabinoid-based compounds (eg, THC, CBD, etc) will not be considered exclusionary.
- 22. Participants with a diagnosis of COPD or other clinically significant lung disease.
- 23. Investigator site staff directly involved in the conduct of the study and their family members, site staff otherwise supervised by the investigator, and sponsor and sponsor delegate employees directly involved in the conduct of the study and their family members.

